This study is designed as a dose-finding study of SUVO compared to placebo. Briefly, OUD patients seeking supervised withdrawal will be admitted into a clinical research unit and stabilized onto buprenorphine before being randomly assigned to study condition. All participants will then undergo a routine buprenorphine taper, followed by a post-taper phase. Participants will be randomized to receive either placebo, SUVO 20mg, or SUVO 40mg and we hypothesize that one or both doses of SUVO will improve total sleep time relative to placebo. The dose of SUVO identified as most efficacious in this study will be used in a subsequent study. This study is supported by power analyses that were conducted for both Aims 1 and 2. Primary outcomes of this study include total sleep time as measured via an ambulatory electroencephalography (EEG) device, wrist actigraphy, and self-reported sleep as well as abuse liability measures of SUVO. Participants will be referred to ongoing treatment following completion of the study and will be provided with opioid overdose education and Narcan as an additional prevention measure.

2. Objectives (include all primary and secondary objectives)

- **Primary Aim 1: Evaluate whether 20mg and 40mg suvorexant, relative to placebo, improves total sleep time among patients undergoing routine opioid withdrawal, assessed via (a) EEG, (b) actigraphy, and (c) self-report.**

- Primary Aim 2: Evaluate the abuse liability of 20mg SUVO versus 40mg SUVO relative to placebo using self-report ratings, and secondary measures that include a hypothetical purchase task and drug ratings.
 - Secondary Aim 1: Evaluate whether 20mg SUVO and 40mg SUVO decreases self-reported measures of drug effects and craving, opioid withdrawal, concomitant medication use, and self-reported stress; decreased diurnal salivary cortisol and serum cortisol/adrenocorticotropic releasing hormone; and improves treatment retention relative to placebo.
3. **Background** (briefly describe pre-clinical and clinical data, current experience with procedures, drug or device, and any other relevant information to justify the research)

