The first primary outcome for this study will be total sleep time during opioid withdrawal as determined by EEG, and supplemented by actigraphy and self-report.

The second primary outcome for this study is abuse liability, which will be assessed via next day measures of Drug Liking measured on a 0-100 point VAS.

b. Secondary outcome variables.

(1) Secondary outcomes from the Sleep Profiler EEG will include measures of sleep continuity and architecture

(2) Secondary actigraphy outcomes will include sleep and activity-related outcomes

(3) Secondary self-report sleep ratings will include self-reported sleep measures

(4) Opioid withdrawal severity, assessed via the subjective opiate withdrawal scale.

(5) Other secondary outcomes include a hypothetical purchasing task, other self-report VAS measures of abuse liability (e.g. drug effect, good effect, bad effect, perceived drug value), self-reported measures of drug craving, VAS opioid withdrawal, stress; diurnal cortisol; vital signs; and retention in treatment.

c. Statistical plan including sample size justification and interim data analysis.

Power Analyses: In order to support the planned 2 and 3 group analyses (comparing 20mg SUVO, 40mg SUVO, and placebo), we used G-power to derive sample sizes from previously reported effect sizes in clinical trials on SUVO and hypothetical opioid purchase task data; both displayed large effect sizes (≥ 0.70). A total sample size of 36 participants (12 per group) would provide 95% power to detect an effect size of 0.70 for difference in total sleep time (Primary Aim 1) and difference in the opioid demand curve (Secondary Aim 1). A study on the abuse liability of SUVO, zolpidem, and placebo in non-ODU patients (Schoedel et al., 2016) reported a medium to large effect size on drug liking (0.45), suggesting a total sample size of 34 would provide 90% power to detect an effect size of 0.45 for Primary Aim 2. To protect against participant drop out, we are proposing to enroll 15 participants per medication group (total N=45).

Analyses: All Primary Outcomes (total sleep time, opioid withdrawal severity, and abuse liability) will be compared as a function of group (20mg SUVO, 40mg SUVO, and placebo; or SUVO [collapsed] vs placebo) and phase (taper vs. post-taper), as well as group by day (7 nights) using 2-factor Proc Mixed analyses with Tukey posthoc testing. Both peak values and Area-under-the-curve (AUC) values of total sleep time, SOWS scores, and Drug Liking

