will be derived for (a) the entire study, (b) the taper period, and (c) the post-taper period. These outcomes will be compared as a function of group and group x phase using independent groups t-tests and ANOVAs with Tukey post-hoc for pairwise comparisons. If data does not meet ANOVA assumptions, mixed model regressions will be used.

Secondary outcomes from the Sleep Profiler EEG may include measures of sleep continuity (sleep latency, sleep efficiency [total sleep time/time spent in bed], wake after onset [WASO], number of awakenings) and architecture (time spent in stage 1, stage 2, stage 3, and rapid eye movement [REM] sleep). (b) Secondary actigraphy outcomes may include wake after sleep onset (WASO), time spent napping, number of naps, and total activity. (c) Secondary self-report ratings may include subjective WASO, VAS sleepiness and quality of sleep, and Stanford Sleepiness Scale score. **Analyses:** All outcomes will be compared as a function of group (20mgSUVO, 40mg SUVO, and placebo) and phase (taper vs. post-taper), as well as group by day (7 nights) using 2-factor Proc Mixed analyses with Tukey posthoc testing. Area-under-the-curve (AUC) values for the entire study and the taper and post-taper periods will then be derived and compared as a function of group and group x phase using independent groups t-tests and ANOVAs with Tukey post-hoc for pairwise comparisons. If data does not meet ANOVA assumptions, mixed model regressions will be used.

Secondary actigraphy outcomes may include wake after sleep onset (WASO), time spent napping, number of naps, and total activity. Secondary self-report ratings may include subjective WASO, visual analogue scale (VAS) sleepiness and quality of sleep, and Stanford Sleepiness Scale score. All outcomes will be compared as a function of group (20mg SUVO, 40mg SUVO, and placebo) and phase (taper vs. post-taper), as well as group by day (7 nights) using area-under-the-curve (AUC). The taper and post-taper periods will then be derived and compared as a function of group and group x phase using independent groups t-tests and ANOVAs with Tukey post-hoc for pairwise comparisons. If data does not meet ANOVA assumptions, mixed model regressions will be used.

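### The 95% power for total sleep time rests on an undefined effect size of 0.70 and, at 0.70 SD, does not cover the planned dose-placebo comparisons

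*Combined protocol and SAP*

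**What the plan says.** The Power Analyses paragraph of Section 7.c opens: "In order to support the planned 2 and 3 group analyses (comparing 20mg SUVO, 40mg SUVO, and placebo), we used G-power". It takes its effect sizes from earlier suvorexant trials and from purchase-task data, calls both large, and concludes: "A total sample size of 36 participants (12 per group) would provide 95% power to detect an effect size of 0.70", applied to the difference in total sleep time (Primary Aim 1). Enrolment is then raised to 15 per group, 45 in all, to allow for dropout.

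The paragraph does not say whether 0.70 is Cohen's f or a standardized mean difference. It also omits the test, alpha, sidedness, the SD of total sleep time, any difference in minutes and any correlation between nights.

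The questions the trial asks are dose against placebo. Primary Aim 1 in Section 2 reads: "Evaluate whether 20mg and 40mg suvorexant, relative to placebo, improves total sleep time". The Abstract says: "we hypothesize that one or both doses of SUVO will improve total sleep time relative to placebo". The Analyses paragraphs of Section 7.c compare "20mg SUVO, 40mg SUVO, and placebo; or SUVO [collapsed] vs placebo" by phase and over 7 nights in mixed models with Tukey tests. They also compare summary values by "independent groups t-tests and ANOVAs with Tukey post-hoc for pairwise comparisons".

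**The concern.** The paragraph offers the calculation in support of both the 2-group and the 3-group analyses and attaches 0.70 to a difference in total sleep time drawn from suvorexant trials. A reader will naturally take 0.70 as a drug-placebo difference in SD units and conclude that each dose-placebo comparison has 95% power to find it. With 12 per arm that cannot be so for a simple comparison of means.

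At stake is how the efficacy result is read. The Abstract says the dose found most efficacious goes forward to a subsequent study, so a dose-placebo comparison that misses significance needs to be read against its own power.

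**Working it through.** **Inputs from Section 7.c.** N = 36, 12 per group; effect size 0.70; stated power 95%; enrolment 15 per group (45); 7 nights; t-tests, ANOVA with Tukey, and pooled suvorexant against placebo.

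**Assumed, because not stated.** Alpha 0.05, two-sided for t-tests; between-night correlation r from 0.3 to 0.8.

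**1. Reproducing the stated figure.** One-way three-group ANOVA, Cohen's f = 0.70, noncentrality N × f²:
- N = 36: 36 × 0.49 = 17.64 on 2 and 33 df, critical F 3.285, power 95.7%.
- N = 33: 33 × 0.49 = 16.17 on 2 and 30 df, power 93.8%.

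Under this reading, 36 is the smallest balanced total that reaches 95%.

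**2. What f = 0.70 means.** f is the SD of the group means divided by the within-group SD.
- Both doses equally above placebo by δ: f = δ√2/3, so δ = 0.70 × 3/√2 = 1.48 SD.
- Evenly spaced means, placebo to 40 mg = δ: f = δ/√6, so δ = 0.70 × √6 = 1.71 SD.

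**3. Power if 0.70 is a standardized mean difference.** Noncentral t, 12 per arm:
- One dose v placebo, t-test: noncentrality 0.70 × √(12/2) = 1.715, 22 df, critical value 2.074.
- One dose v placebo, Tukey: same noncentrality, 33 df, critical value 3.470/√2 = 2.454.
- Pooled 24 v 12: 0.70 × √(24 × 12/36) = 1.980, 34 df, critical value 2.032.
- Omnibus F: f = 0.70 × √2/3 = 0.330 (doses equal) or 0.70/√6 = 0.286 (evenly spaced).

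| Test at 0.70 SD | N = 36 | N = 45, all analysed |
|---|---|---|
| One dose v placebo, Tukey | 24.5% | 31.5% |
| One dose v placebo, t-test | 37% | 46% |
| Pooled suvorexant v placebo | 48.6% | 58.1% |
| Omnibus F | 29-38% | 36-47% |

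**4. Power if 0.70 is in single-night SD units and seven nights are averaged.** The SD of a seven-night mean is the single-night SD × √((1 + 6r)/7), so the effect becomes 0.70/√((1 + 6r)/7). This is 0.77 at r = 0.8 and 1.11 at r = 0.3.

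| Test, N = 36 | r = 0.8 | r = 0.5 | r = 0.3 |
|---|---|---|---|
| One dose, Tukey | 30% | 44% | 60% |
| One dose, t-test | 44% | 58% | 74% |
| Pooled | 56% | 72% | 86% |

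**5. Difference detectable at 80% power, 12 per arm.** Solving the step 3 formulas for the difference gives about 1.2 SD (unadjusted t-test), 1.35 SD (Tukey) and 1.02 SD (pooled 24 v 12).

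**The case against.** **The 95% may be right for the test the sponsor had in mind.** This stands. If f = 0.70 was intended, 95.7% is correct arithmetic. A reader might infer that the sponsor used the wrong metric or that the figure is a miscalculation; the documents support neither, because they never define the metric and the source effect sizes cannot be checked here.

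**The one-way omnibus test is not the only route to 95%.** This also stands. A group-by-phase interaction with three groups, two phases, f = 0.35 (half of 0.70) and an assumed correlation of 0.5 has noncentrality 36 × 2 × 0.35²/0.5 = 17.64 on 2 and 33 df, hence the same 95.7%. Group by phase is a planned analysis. It tests whether the groups' difference changes between phases, so it supplies no power for the dose-placebo difference itself.

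**The Aim 2 figure does not support the omnibus reading.** For 0.45, N = 34 and 90% power, a one-way omnibus test with f = 0.45 gives only 60%. A group-by-night interaction over seven nights (f = 0.225, assumed r = 0.5) comes closer, at 91.5%. Cohen's f in a one-way test is therefore a match for Aim 1, not an established fact.

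**Repeated nights and full retention help.** They do, but not enough within the range shown. With all 45 analysed and nights averaged at r = 0.8 to 0.3, the pooled contrast has 66-93%. It passes 95% only at lower correlation (97% at r = 0.2). A single-dose comparison with 12 per arm needs r of about 0.05 or less. Adjusting for baseline at an assumed correlation of 0.5 gives 33-60% across the three comparisons at N = 36.

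**A reader might infer that the trial would miss a 0.70 SD effect more often than not.** That is too general. It holds for the three comparisons in step 3 at N = 36, but the pooled contrast with all 45 analysed has 58%. Nor does any section say that a null result would be taken as evidence against suvorexant.

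**Conclusion.** The point holds as a defect of definition and scope. The 95% is tied to an effect size whose metric and test are not given. If 0.70 means 0.70 SD of the analysed outcome, the comparisons that answer Primary Aim 1 have about 25% to 37% power for one dose and 49% for pooled doses at N = 36, or about 32% to 46% and 58% if all 45 are analysed. If 0.70 is a single-night effect, seven-night averages at N = 36 stay between 30% and 86% over the assumed correlations.

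The 95% does match an omnibus test, but for gaps of about 1.5 to 1.7 SD, and the text does not tell the reader so. These results rest on an assumed alpha of 0.05 (two-sided for t-tests) and, for the repeated nights, on the assumed range of r. The conclusion does not depend on which metric was intended: under either reading, the 95% should not stand as the power of the dose-placebo comparisons at 0.70 SD.

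**What to change.** In the Power Analyses paragraph of Section 7.c:

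- State the metric of 0.70, the test, alpha with sidedness, and any between-night correlation used to obtain 95%, and limit the 95% to that test. The sponsor should report what was actually run; the review cannot supply it. The same details are needed for the Aim 2 figure.
- For one dose against placebo and for pooled suvorexant against placebo, replace the 95% with each comparison's own power at 0.70 SD. Alternatively, give the difference detectable at 80% power with 12 per arm: about 1.2 SD (unadjusted t-test), 1.35 SD (Tukey) or 1.02 SD (pooled 24 v 12). Label each by test and convert it to minutes with a stated SD of total sleep time, which the documents do not give.

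This costs protocol wording only. Sample size, treatment and data collection are unchanged. The downside is a less favourable stated figure.

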Buprenorphine: Buprenorphine is FDA-approved for the treatment of OUD and it will be used according to that indication in this study. The buprenorphine stabilization and taper will be open label. Participants will be stabilized on buprenorphine for a maximum 3 week period before study admission, and will then complete a 3-day stabilization period (e.g., 8-16mg/day) and a 4-day step-wise taper. These approaches are standard clinical practice. This study utilized the open label taper approach in order to increase ecological validity of the supervised withdrawal paradigm.

Concomitant Medications: Consistent with standard clinical practice treatment, the following concomitant medications will be available to patients upon request: ibuprofen, acetaminophen, loperamide, milk of magnesia, and simethicone. Clonidine may be provided during the induction period only. Concomitant medications introduce a necessary confound in opioid withdrawal research because they reduce the withdrawal symptom severity that is being evaluated as part of the primary study outcomes. However, our considerable experience with opioid withdrawal studies suggests that provision of some additional supportive medications is necessary to prevent treatment attrition. Following randomization to experimental group, patients will not receive additional sleep aids or clonidine. Concomitant medication use will be PRN and compared across groups as an outcome.

- b. Justification and safety information if FDA approved drugs will be administered for non-FDA approved indications or if doses or routes of administration or participant populations are changed.

Suvorexant (SUVO): Suvorexant is approved by the FDA for the indication of insomnia at a 10mg and 20mg dose, so an IND will be requested from the FDA for the doses (20mg, 40mg) proposed in this trial. The proposed 40mg dose is being evaluated because suvorexant has a broad therapeutic window, persons with OUD might have increased orexin signaling, as evidenced by postmortem studies citing 54% more orexinergic neurons in the lateral hypothalamus of persons with OUD compared to healthy controls, and because sleep disturbance during opioid withdrawal is severe and- as of yet- no sleep-promoting pharmacotherapies have been shown to be effective in human opioid withdrawal studies.

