Secondary measures will be additional ratings on the hypothetical purchase task, SOWS and VAS ratings of opioid withdrawal, VAS ratings of abuse liability, self-reported craving, self-reported stress, perceived drug value, and diurnal salivary cortisol (measured via AUC values and mean daily cortisol) and cortisol/ACTH ratios. Purchase task data will be fit to opioid demand curves for comparison. **Analyses:** All outcomes will be compared as a function of group (20mg SUVO, 40mg SUVO, and placebo) and phase (taper vs. post-taper), as well as group by day (7 nights) using area-under-the-curve (AUC). The taper and post-taper periods will then be derived and compared as a function of group and group x phase using independent groups t-tests and ANOVAs with Tukey post-hoc for pairwise comparisons. If data does not meet ANOVA assumptions, mixed model regressions will be used. Exploratory analyses will include linear and multivariate regression models to examine the relationship between measures of sleep, stress, opioid withdrawal, and craving. Logistic regression will be used to examine the relationship between sleep, stress, opioid withdrawal, and craving on the likelihood of treatment attrition.

d. Early stopping rules.

Patients will discontinue their study participation if they request to be discharged, have a serious adverse event, or if the study physicians decide it is in the patient's best interest to be removed from the study. All patients will be discharged with naloxone, opioid overdose education, and referral to outpatient OUD treatment.

8. Risks

a. Medical risks, listing all procedures, their major and minor risks and expected frequency.

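### Section 7.c treats opioid withdrawal severity as primary although 7.a and 7.b do not, and names neither a deciding analysis nor an alpha for total sleep time

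*Combined protocol and SAP*

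**What the plan says.** **Outcome status.** Section 7.a defines two primary outcomes. The first is "total sleep time during opioid withdrawal as determined by EEG, and supplemented by actigraphy and self-report"; the second is abuse liability, measured by next-day Drug Liking. Section 7.b(4) lists as secondary "Opioid withdrawal severity, assessed via the subjective opiate withdrawal scale". Secondary Aim 1 in section 2 agrees, asking whether suvorexant "decreases self-reported measures of drug effects and craving, opioid withdrawal, concomitant medication use, and self-reported stress".

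The Analyses paragraph of 7.c then says "All Primary Outcomes (total sleep time, opioid withdrawal severity, and abuse liability) will be compared as a function of group". Section 6.a, on concomitant medications, says that "they reduce the withdrawal symptom severity that is being evaluated as part of the primary study outcomes".

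Two related labels also disagree:
- Section 4.a (Abuse Liability Measures) assigns abuse liability to a Primary Aim 3, but section 2 has only two Primary Aims, with abuse liability as the second.
- The Abstract says "Primary outcomes of this study include total sleep time as measured via an ambulatory electroencephalography (EEG) device, wrist actigraphy, and self-reported sleep", and Primary Aim 1 has sleep time "assessed via (a) EEG, (b) actigraphy, and (c) self-report". Both set the three instruments side by side, whereas 7.a puts EEG first.

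**Analysis of total sleep time.** Section 7.c compares three groups or, alternatively, collapsed suvorexant with placebo. It uses mixed models by phase and by day (7 nights). It then applies t-tests and ANOVAs to both peak and AUC values over the entire study, the taper and the post-taper period. Tukey is named for pairwise comparisons. No analysis is designated as deciding, and no significance level or sidedness appears anywhere.

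**The concern.** The Abstract states a directional hypothesis: one or both doses lengthen total sleep time relative to placebo. The sample size is justified at 95% power for that outcome. For such a claim to be confirmatory, the outcome, contrast, summary, window and alpha must be fixed before the data are seen.

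As the text stands, a withdrawal-severity result could be presented as primary or as secondary once it is known. The contrast, summary or window most favourable to suvorexant could likewise be presented as the primary sleep result. Tukey does not prevent this, because it covers only the pairwise comparisons inside one analysis. The 95% power also cannot be attached to a test while the test is open.

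**Working it through.** **1. Outcome status, side by side.**

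| Place | Withdrawal severity |
|---|---|
| 7.a | not among the two primaries |
| 7.b(4) | secondary |
| Section 2, Secondary Aim 1 | secondary |
| 7.c, Analyses paragraph | primary |
| 6.a, Concomitant Medications | part of the primary outcomes |
| 7.c, Power Analyses | not covered (total sleep time, demand curve and Drug Liking only) |

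The later 7.c sentence "Secondary measures will be additional ratings on the hypothetical purchase task, SOWS and VAS ratings of opioid withdrawal" also points to secondary. It could, however, mean only additional ratings on each of those scales, so no weight is put on it.

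**2. The entire-study window.** The stay is 11 days and 10 nights (4.a). It comprises 3 stabilization days (6.a), 4 taper days, and 4 post-taper days with 3 nights. The 7 nights in 7.c equal 4 taper + 3 post-taper. Dosing starts the evening before Taper Day 1, so 7 + 1 = 8 nights are dosed. The phrase could mean 7 or 8 nights.

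**3. The plan's own power figure.** Inputs from 7.c: N = 36 (12 per group), effect size 0.70, power 95%. Alpha 0.05 is assumed. Reading 0.70 as Cohen's f in a three-group omnibus F test:
- λ = f²N = 0.49 × 36 = 17.64, with 2 and 33 degrees of freedom and critical F = 3.285.
- Power = 95.7%, so the stated 95% reproduces.

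Reading 0.70 as Cohen's d does not reproduce it: a two-sided t-test gives 37.5% for 12 v 12 and 48.6% for 12 v 24.

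**4. False claims favouring suvorexant.** Assumptions, because the documents give no values: two-sided 0.05, no true effect, normal complete data, 7 nights, and equal night-to-night correlation of 0.3 to 0.7, with 12 or 15 per group. A claim means that either dose beats placebo by Tukey, or that collapsed suvorexant beats placebo.

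Analytic anchor for one Tukey analysis (12 per group): the critical t is 3.470/√2 = 2.454, with one tail P(t₃₃ > 2.454) = 0.98%. Two doses give at most 2 × 0.98 = 1.96%, and their overlap through the shared placebo arm brings this to about 1.8%. One collapsed contrast gives one tail of 5%, that is 2.5%.

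Simulation, 40,000 replicates per setting:

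| What may be reported as primary | False claim |
|---|---|
| Tukey or collapsed; AUC or peak; any of 3 windows | 5.7–8.8% |
| As above, without peak | 4.2–5.7% |
| Tukey only; AUC or peak; any window | 3.6–5.7% |
| Tukey only; AUC; any window | 2.6–3.6% |
| Whole-period AUC; Tukey or collapsed | about 3% |
| One Tukey analysis named in advance | about 1.8% |
| One collapsed analysis named in advance | about 2.5% |

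At correlation 0.9 the first row falls to 4.4–4.6%. With correlation that decays between nights (AR1 of 0.5, 0.7 and 0.9; 12 per group) it is 9.7%, 8.7% and 6.1%.

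**5. Power depends on the contrast.** One summary value per participant, 12 per group, two-sided 0.05. If f = 0.70 with one group differing from the other two, the dose-placebo difference is d = 0.70 × 3/√2 = 1.48.

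| Effect | Tukey, either dose v placebo | Collapsed v placebo |
|---|---|---|
| f = 0.70, both doses work | 95% | 98% |
| f = 0.70, one dose works | 88% | about 40% |
| d = 0.70, both doses work | 37% | 49% |
| d = 0.70, one dose works | 25% | 14% |

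**The case against.** The strongest reply is that this is a 45-person dose-finding study feeding a later trial. Section 7.a already settles the lead instrument, Tukey is specified, no interim look is planned, and most of the narrower selection scenarios lie near or below 5%. All of that is correct, and it limits the size of the problem. It does not remove it. The study states a hypothesis, labels outcomes primary and claims 95% power, while 7.b and 7.c, in the same section, disagree on what is primary. Section 6.a is only a rationale sentence and adds little; the conflict stands without it.

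A reader might infer more than the documents support:
- **That the entire study could mean all 10 residential nights.** Section 7.a restricts the outcome to sleep during withdrawal, and 4.a describes the stabilization EEG as baseline data. The open choice is 7 or 8 nights.
- **That the error rate is 15–26%.** Counting any p < 0.05 at 15 per group gives 14.5–20.5% over 12 tests, and 21.7–26.4% with the interaction tests. Those counts include omnibus results and results against suvorexant, which would not support the stated hypothesis.
- **That the instrument is wholly open or multiplicity uncontrolled.** Section 7.a says EEG, and Tukey works within each analysis.
- **That the choice of dose is compromised.** The documents tie that choice to no test.

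**Conclusion.** The point holds on the text and should be fixed. The status of withdrawal severity is contradictory between 7.a/7.b and 7.c, and total sleep time has several planned analyses with no deciding one and no alpha. Confidence in this is high, because it does not rest on the simulation.

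The size is illustrative and moderate: about 6–9% false claims under unrestricted selection, which is the top of the scenarios examined and not an expected rate. It rests on the assumed alpha, correlation and complete data. The mixed models, the interactions, the other two sleep instruments and the 7-or-8-night question are not counted, and the contradiction over withdrawal severity contributes nothing to these percentages.

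**What to change.** Before unblinding:

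1. Reconcile the list of primary outcomes across the 7.c Analyses paragraph, 6.a, the Primary Aim 3 label in 4.a, the Abstract and Primary Aim 1. Since 7.a is the defining section, following it makes withdrawal severity (SOWS) secondary, EEG total sleep time primary, and actigraphy and self-report supplementary.
2. In 7.c, state the alpha and sidedness, and name one deciding analysis for each primary outcome. For EEG total sleep time this could be a mixed model over the taper and post-taper nights with three groups and Tukey dose-placebo contrasts. A collapsed contrast is also valid if named in advance, but the three-group form fits the one-or-both-doses hypothesis better. Do the same for Drug Liking. Label every other contrast, summary and window supportive.
3. Define the entire-study window, including whether the dosed night before Taper Day 1 counts.
4. Say whether 0.70 is f or d, and restate the power for the named test. The present 95% belongs to a three-group omnibus test with f = 0.70 at an assumed alpha of 0.05.

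Cost: text changes only, with no change to sample size or data collection. Fewer results can be called primary. The restated power may be less comfortable: with Tukey contrasts about 95% if both doses work and 88% if only one does under f = 0.70, or about 37% and 25% if 0.70 is Cohen's d. Those figures use one summary value per participant and would need recalculating for a 7-night mixed model.
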